#### 4.1.1 Entinostat

Entinostat is an oral agent. Entinostat should be taken on an empty stomach (fasting) either at least 1 hour prior to a meal or at least 2 hours after a meal. The tablets should be taken one at a time. The tablets should not be split, crushed or chewed. Entinostat is known to cause nausea and vomiting. To reduce the incidence of nausea and vomiting associated with entinostat administration, patients will be instructed to take a 5-HT3 antagonist orally or IV 30-60 minutes prior to taking the dose of entinostat.

#### 4.1.2 Azacitidine

Azacitidine is supplied as 100 mg of white, lyophilized powder with 100 mg of mannitol, USP in 30 ml flint vials. The contents of each vial should be dissolved in 4mL of sterile water or 0.9% sodium chloride to provide a 25 mg/ml slurry. Azacitidine does not go into solution but forms a loose slurry when reconstituted in this fashion. Reconstituted solutions of azacitidine are unstable. Upon reconstitution, the material should be injected within 60 minutes. The slurry should be injected subcutaneously. The slurry SHOULD NOT be injected intravenously. Doses may be split into multiple injection sites if volume to be administered is too large. Injection sites should be rotated on a daily basis.

#### 4.1.3 Nivolumab

Nivolumab vials are to be stored at a temperature of 2°C to 8°C and should be protected from light. If stored in a glass front refrigerator, vials should be stored in the carton. Recommended safety measures for preparation and handling of BMS-936558 include laboratory coats and gloves. After Nivolumab been prepared for administration, the total storage time (combination of refrigeration and room temperature) is not to exceed 24 hours. Stability data for Nivolumab following dilution and transfer to the IV bag supports either: 24 hours at 2°C to 8°C in the

refrigerator, or 4 hours at room temperature/under room light and 18 hours at 2°C to 8°C in the refrigerator. Care must be taken to assure sterility of the prepared solution as the product does not contain any anti-microbial preservative or bacteriostatic agent. No incompatibilities between Nivolumab and polyolefin bags have been observed.

Nivolumab will be administered as an IV infusion as close to 30 minutes as possible, using a volumetric pump with a 0.2 micron in-line filter, followed by a saline flush.

Nivolumab will be administered as a flat 240 mg dose or 480 mg every 4 weeks once the completion of cycle 6 has occurred. There will be no dose escalations or reductions of nivolumab allowed. Subjects may be dosed no less than 12 days from the previous dose. There are no premedications recommended for Nivolumab on the first cycle. If an allergic reaction is noted, then acetaminophen 650 mg PO and diphenhydramine 50 mg PO/IV may be administered prior to Nivolumab infusion.

#### **4.2 General concomitant medication and supportive care guidelines**

- 4.2.1 No investigational or commercial agents or therapies other than those described above may be administered with the intent to treat the malignancy.
- 4.2.2 Contraceptive therapy: Sexually active men and women of child-bearing potential must agree to use effective contraception.
- 4.2.3 Concomitant use of valproic acid is prohibited due to its known activity as a histone deacetylase inhibitor.
- 4.2.4 Nausea and vomiting after entinostat administration are expected. Prophylactic 5-HT3 inhibitors will be administered at least 30 minutes prior to ingestion of entinostat as well as on an as needed basis. Delayed nausea and vomiting is associated with azacitidine 4-6 hours after treatment. Prophylactic 5HT3 inhibitor will be administered 30 minutes prior to injection of azacitidine on days 1-5, and 8-10. Prochlorperazine and/or 5HT3 inhibitor may also be taken for delayed nausea as needed.
- 4.2.5 Diarrhea: **If diarrhea occurs during Nivolumab treatment, workup and treatment should follow the Nivolumab diarrhea toxicity treatment algorithm located in the appendix of the Nivolumab investigators brochure.**
- 4.2.6 Neutropenia without fever: The clinical situation should be closely followed for fever, focal signs of infection, and neutrophil nadir.
- 4.2.7 Neutropenia with fever: Hospitalization and urgent broad-spectrum antibiotics are required for this potentially life-threatening complication. The occurrence of a temperature higher than 38.3°C (100.9°F) demands prompt evaluation of blood counts and examination for source of infection.
- 4.2.8 Anemia: Red blood cell support should be given for any patient with symptomatic

anemia and is recommended for patients with asymptomatic anemia when hemoglobin is below 8 g/dL. Erythropoietin or darbepoietin may be used at the discretion of the investigator.

- 4.2.9 Thrombocytopenia: Platelet transfusion should be given for a platelet count below 10,000/mm^3 in the absence of bleeding. If bleeding develops or invasive procedures are planned, platelet transfusion should be administered in accordance with standard practice.
- 4.2.10 Constipation: Constipation has been a common side effect of azacitidine and entinostat. Treatment with stool softeners and laxatives should be initiated early on to prevent symptoms from constipation.
- 4.2.11 The following medications are prohibited during the study (unless utilized to treat a drug-related adverse event): immunosuppressive agents, immunosuppressive doses of systemic corticosteroids (except as noted in inclusion/exclusion section), Subjects are permitted to use topical, ocular, intra-articular, intranasal, and inhaled corticosteroids (with minimal systemic absorption). Physiologic replacement doses of systemic corticosteroids (eg prednisone  $\leq$  10 mg/day) are permitted. A brief (less than 3 weeks) course of corticosteroids for prophylaxis (eg, contrast dye allergy) or for treatment of non-autoimmune conditions (eg, delayed-type hypersensitivity reaction caused by a contact allergen) is permitted. Sensitive substrates of CYP1A2, CYP2C8, CYP3A with a narrow therapeutic window are prohibited (including: Theophylline, tizanidine, paclitaxel, alfentanil, astemizole, cisapride, cyclosporine, dihydroergotamine, ergotamine, fentanyl, pimozide, quinidine, sirolimus, tacrolimus and terfenadine). Drugs that are known to inhibit or induce P-gp are prohibited (including: amiodarone, azithromycin, captorpril, carvedilol, clarithromycin, conivaptan, diltiazem, dronedarone, felodipine, lopinavir, quercetin, ranolazine, ticagrelor, ritonavir, cyclosporine, verapamil, erythromycin, ketoconazole, itraconazole, quinidine, avasimibe, carbamazepine, phenytoin, rifampin, St. John's Wort, and tipranavir/ritonavir)
- 4.2.12 Non-palliative radiation therapy is not allowed. Palliative radiation therapy is only allowed during Nivolumab monotherapy, not during concurrent epigenetic therapy, if deemed necessary for the patient by the investigator. Palliative radiation therapy to the lung is not recommended.

If palliative radiotherapy is required, and the patient is currently receiving concurrent epigenetic therapy, the epigenetic therapy must be held. Upon completion of the palliative XRT, the patient may be allowed to resume study treatment with epigenetic therapy and nivolumab following the 1 week washout period.

If the patient is on single agent Nivolumab therapy when they require palliative radiation therapy, then Nivolumab should be withheld for at least 1 week before, during and 1 week after radiation. Patients should be closely monitored for any potential toxicity during and after receiving radiotherapy, and AEs should resolve to grade  $\leq$  1 prior to resuming Nivolumab.

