#### **4.4.1 Treatment Beyond Disease Progression**

Treatment beyond disease progression is allowed for patients receiving concurrent azacitidine, entinostat and nivolumab on Arm D, Arm E and Arm F. If disease progression (PD) is noted during the 6 cycles of concurrent therapy per RECIST 1.1, the patient may continue study treatment until disease progression is confirmed. If at that time disease progression (PD) is confirmed, the patient will come off study treatment. After 6 concurrent cycles, patients will continue nivolumab monotherapy treatment irrespective of disease

progression status, and will follow the decision to treat beyond disease progression (PD) as per below. If the noted PD requires palliative radiation therapy, please see Section 4.2.12 regarding subsequent study treatment.

Subjects being currently treated with nivolumab monotherapy on any study Arm will be permitted to continue treatment beyond initial RECIST 1.1 defined PD as long as they meet the following criteria:

1. Investigator-assessed clinical benefit, and do not have rapid disease progression
2. Continue to meet all other study protocol eligibility criteria
3. Tolerance of the study drug
4. Stable performance status
5. Treatment beyond progression will not delay an imminent intervention to prevent serious complications of disease progression (e.g. CNS metastasis)

The decision to continue treatment beyond initial progression must be documented in the study records.

A radiographic assessment/scan will be performed at the end of the cycle following the original PD to determine whether there has been a decrease in the tumor size or continued PD. The assessment of clinical benefit should be balanced by clinical judgment as to whether the subject is clinically deteriorating and unlikely to receive any benefit from continued treatment with nivolumab.

If the investigator feels that the patient receiving nivolumab monotherapy continues to achieve clinical benefit by continuing treatment, the subject may remain on the trial and continue to receive monitoring according to the Study calendar.

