#### 9.1.2 Disease Parameters

To assess objective response or future progression, it is necessary to estimate the overall tumor burden at baseline and use this as a comparator for subsequent measurements. Measurable disease is defined by the presence of at least one measurable lesion.

Measurable disease. Measurable lesions are defined as those that can be accurately measured in at least one dimension (longest diameter to be recorded) as  $\geq 20$  mm by chest x-ray or as  $\geq 10$  mm with CT scan, MRI, or calipers by clinical exam. All tumor measurements must be recorded in millimeters (or decimal fractions of centimeters).

Note: Tumor lesions that are situated in a previously irradiated area are not considered measurable unless there has been demonstrated progression in the lesion.

Malignant lymph nodes. To be considered pathologically enlarged and measurable, a lymph node must be  $\geq 15$  mm in short axis when assessed by CT scan (CT scan slice thickness recommended to be no greater than 5 mm). At baseline and in follow-up, only the short axis will be measured and followed.

Non-measurable disease. All other lesions (or sites of disease), including small lesions (longest diameter  $<10$  mm or pathological lymph nodes with  $\geq 10$  to  $<15$  mm short axis), are considered non-measurable disease. Bone lesions, leptomeningeal disease, ascites, pleural/pericardial effusions, lymphangitic involvement of the skin or lung, inflammatory breast disease, and abdominal masses/abdominal organomegaly (not followed by CT or MRI), are considered as non-measurable.

Note: Cystic lesions that meet the criteria for radiographically defined simple cysts should not be considered as malignant lesions (neither measurable nor non-measurable) since they are, by definition, simple cysts.

'Cystic lesions' thought to represent cystic metastases can be considered as measurable lesions, if they meet the definition of measurability described above. However, if non-cystic lesions are present in the same patient, these are preferred for selection as target lesions.

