#### 9.1.4.3 Evaluation of Best Overall Response

The best overall response is the best response recorded from the start of the treatment until disease progression/recurrence (taking as reference for progressive disease the smallest measurements recorded since the treatment started). The patient's best response assignment will depend on the achievement of both measurement and confirmation criteria.

| Target Lesions | Non-Target Lesions          | New Lesions | Overall Response | Best Overall Response when Confirmation is Required* |
|----------------|-----------------------------|-------------|------------------|--|
| CR             | CR                          | No          | CR               | >4 wks. Confirmation**                               |
| CR             | Non-CR/Non-PD               | No          | PR               | >4 wks. Confirmation**                               |
| CR             | Not evaluated               | No          | PR               |  |
| PR             | Non-CR/Non-PD/not evaluated | No          | PR               |  |
| SD             | Non-CR/Non-PD/not evaluated | No          | SD               | Documented at least once >4 wks. from baseline**     |
| PD             | Any                         | Yes or No   | PD               | no prior SD, PR or CR                                |
| Any            | PD***                       | Yes or No   | PD               |  |
| Any            | Any                         | Yes         | PD               |  |

\* See RECIST 1.1 manuscript for further details on what is evidence of a new lesion.

\*\* Only for non-randomized trials with response as primary endpoint.

\*\*\* In exceptional circumstances, unequivocal progression in non-target lesions may be accepted as disease progression.

**Note:** Patients with a global deterioration of health status requiring discontinuation of treatment without objective evidence of disease progression at that time should be reported as "*symptomatic deterioration*." Every effort should be made to document the objective progression even after discontinuation of treatment.

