#### Simulation Results for Arm D

| Scenario | Assumed true response rate | Pr(Stop for inferiority) | Average # patients treated (10%, 25%, 50%, 75%, 90%) |
|----------|----------------------------|--------------------------|--|
| 1        | 0.1                        | 0.876                    | 15.4 (10, 10, 15, 20, 20 )                           |
| 2        | 0.15                       | 0.662                    | 17.3 (10, 15, 20, 20, 20 )                           |
| 3        | 0.2                        | 0.434                    | 18.51 (10, 20, 20, 20, 20 )                          |
| 4        | 0.25                       | 0.243                    | 19.25 (20, 20, 20, 20, 20 )                          |
| 5        | 0.3                        | 0.119                    | 19.61 (20, 20, 20, 20, 20 )                          |
| 6        | 0.35                       | 0.047                    | 19.86 (20, 20, 20, 20, 20 )                          |
| 7        | 0.4                        | 0.021                    | 19.92 (20, 20, 20, 20, 20 )                          |
| 8        | 0.45                       | 0.008                    | 19.96 (20, 20, 20, 20, 20 )                          |
| 9        | 0.5                        | 0.002                    | 19.99 (20, 20, 20, 20, 20 )                          |

For Arms E and F, respectively, we take the expected ORR to be virtually 0% if epigenetic therapy does not increase the clinical effectiveness of nivolumab alone. We would consider the addition of epigenetic therapy encouraging if the ORR is at least 10%. The study will stop for futility if we see 0 responses among the first 15 patients. We will not consider an

Arm promising if none of the 20 patients on that Arm responds. The following table provides the operating characteristics for Arms E and F, respectively, based on 5000 simulations.

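### Section 4.2.12 both restricts palliative radiation to nivolumab monotherapy and provides for it during concurrent therapy, and the response rules do not cover a target lesion irradiated on study before progression

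*Combined protocol and SAP*

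**What the plan says.** **Radiation on study.** Section 4.2.12 opens its rule on palliative radiation with "Palliative radiation therapy is only allowed during Nivolumab monotherapy, not during concurrent epigenetic therapy". The paragraph after it reads "If palliative radiotherapy is required, and the patient is currently receiving concurrent epigenetic therapy, the epigenetic therapy must be held", and continues: "Upon completion of the palliative XRT, the patient may be allowed to resume study treatment with epigenetic therapy and nivolumab", after a one-week washout. The third paragraph concerns patients on nivolumab alone: "Nivolumab should be withheld for at least 1 week before, during and 1 week after radiation". Section 4.4.1 refers patients back to these rules: "If the noted PD requires palliative radiation therapy, please see Section 4.2.12 regarding subsequent study treatment".

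**Response.** The primary endpoint is the RECIST 1.1 response rate by arm. Section 9.1.4.1 defines a partial response as a fall of at least 30% from baseline in the sum of target-lesion diameters. Section 9.1.4.3 sets the window: "The best overall response is the best response recorded from the start of the treatment until disease progression/recurrence". The one note on irradiated lesions is in the definition of measurable disease in Section 9.1.2: "Tumor lesions that are situated in a previously irradiated area are not considered measurable unless there has been demonstrated progression in the lesion".

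**Decision rule.** For Arms E and F, Section 10.4 takes the response rate to be essentially zero if the epigenetic drugs add nothing, and calls 10% or more encouraging. It then says "The study will stop for futility if we see 0 responses among the first 15 patients", and an arm with no responder among 20 is not considered promising.

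**The concern.** There are two separate problems.

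The first is operational. A site with a patient in cycles 1 to 6 who needs palliative radiation finds one sentence that excludes it and another that explains how to proceed. The site also cannot tell whether nivolumab is interrupted in that phase.

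The second concerns the primary endpoint. Radiation is local anticancer treatment, and it may be aimed at a lesion that is in the target sum. If that lesion shrinks enough, the sum can fall by 30% for a reason unrelated to azacitidine, entinostat or nivolumab. Nothing in the definitions of evaluability, partial response or best overall response says how to treat that assessment. Where the futility bar is a single response, one such case would carry an inactive regimen past it.

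**Working it through.** **A. Section 4.2.12, paragraph by paragraph**

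- Paragraph 1: palliative radiation in the nivolumab-alone phase only.
- Paragraph 2: radiation in the concurrent phase, with the epigenetic drugs held. Only these drugs are named as held, but both they and nivolumab are named as resuming.
- Paragraph 3: in the nivolumab-alone phase, nivolumab is withheld before, during and after radiation.

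Paragraphs 1 and 2 cannot both be followed as worded. Paragraph 2 does not settle nivolumab: the hold names one component, while the resumption implies that both were stopped.

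**B. Would a radiation-driven partial response count?**

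- Section 9.1.1 (evaluable for response): measurable disease, at least one cycle and a re-evaluation. Radiation is not mentioned.
- Section 9.1.4.1 (partial response): a 30% fall in the sum, with no exception for an irradiated lesion.
- Section 9.1.4.3 (window): closes at progression, not at radiation.
- Section 4.6 (removal from treatment): lists other anticancer drugs, not radiation.
- Section 9.1 (confirmation): a repeat scan at least 4 weeks later. This does not help if the shrinkage persists.

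So, for radiation given before progression (for symptoms, say), the rules as written would count the response.

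**C. The plan's own figures for Arms E and F**

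Inputs from Section 10.4: stop at 0 of 15; not promising at 0 of 20. An arm with a response in its first 15 patients cannot finish at 0 of 20, so the first look fixes the table.

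Pr(stop) = (1 − p)^15; average N = 15 × Pr(stop) + 20 × (1 − Pr(stop)).

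At p = 0.10: 0.90^15 = 0.2059, and average N = 18.97. The plan gives 0.206 and 18.97. All nine stopping probabilities in the table reproduce to within 0.003.

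**D. Effect of radiation-driven responses**

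Assume no drug activity and a per-patient probability r of a counted, radiation-driven partial response. The documents give no r, so a range is shown.

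| r | At least 1 of 15: 1 − (1 − r)^15 | At least 1 of 20: 1 − (1 − r)^20 |
|---|---|---|
| 0.5% | 7.2% | 9.5% |
| 1% | 14.0% | 18.2% |
| 2% | 26.1% | 33.2% |
| 5% | 53.7% | 64.2% |

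With a true response rate of 2.5%, the chance of passing the 15-patient look is 1 − [0.975 × (1 − r)]^15. It is 31.6% at r = 0, 41.2% at 1%, 49.5% at 2% and 68.3% at 5%.

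**E. What one response means at the end**

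1/20 = 5%, exact 95% interval 0.1% to 24.9%. That is half the 10% called encouraging. Arm D is less exposed: it needs at least 4 of 20.

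**The case against.** **Paragraph 1 as a no-overlap rule.** It may mean only that radiation and epigenetic drugs are not given together, with paragraph 2 putting this into practice. That is a fair guess at the intent, but limiting radiation to the monotherapy phase does not say it. The need to reconcile stands.

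**Nivolumab.** A reader might infer that nivolumab continues through radiation in the concurrent phase. The documents do not establish this, because paragraph 2 speaks of resuming nivolumab after the washout. The text is ambiguous; it does not prescribe a different rule.

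**Radiation given for progression.** A reader might infer that the Section 4.4.1 route lets shrinkage after progression become a response. Best response closes at progression, so that shrinkage should mostly fall outside the window. The confirmation of progression in Section 4.4.1 governs whether treatment continues. Section 9.1 does ask for progression to be confirmed, so some ambiguity remains, but no text says that an unconfirmed progression is erased for the response rate.

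**Few cases.** Non-palliative radiation is barred, and palliative radiation to the lung is advised against. Bone lesions are non-measurable. Up to five target lesions represent all involved organs, and their whole sum must fall by 30% without new lesions and with confirmation. In an inactive arm, patients who progress early cannot contribute, so a constant r over all 15 is generous. All of this stands, and it argues for the low end of the range.

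**The Section 9.1.2 note.** It could be stretched to radiation given on study. It does not say so, and it gives no instruction on the sum.

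**The remedy can lose a true response.** This also stands. It is costed under the fix.

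**Conclusion.** The point holds in two parts. Section 4.2.12 gives inconsistent instructions on palliative radiation in the concurrent phase and is unclear about nivolumab there. The response rules also lack any provision for a target lesion irradiated on study before progression, and followed literally they would count its shrinkage.

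The size rests on r, which is assumed. The chance that an inactive arm (E or F) passes its 15-patient look is 7% at r = 0.5%, 14% at 1% and 54% at 5%. The restrictions above suggest that r is small.

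A reader might infer that one such response would reverse the conclusion for an arm. The documents do not support that. One response avoids the futility stop and the not-promising label, but 1 of 20 is below the encouraging level, and Section 10.2 makes the final analysis descriptive, with confidence intervals. The harm is an arm wrongly continued and a response rate with an unclear cause. This should be fixed; it does not undermine the design.

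**What to change.** 1. **Section 4.2.12.** The sponsor must reconcile the three paragraphs so that one statement covers each treatment phase and each study drug. Which clinical rule applies is for the sponsor to decide.
2. **Section 9.1.4.3.** Add an endpoint rule, applied to the primary response rate and to the counts in Section 10.4. Once a target lesion is irradiated on study:
   - later assessments cannot establish or confirm a complete or partial response;
   - best response is taken from earlier scans;
   - the lesion is not dropped from the sum to create a response;
   - its shrinkage does not undo a recorded progression for the endpoint.
3. **Data and reporting.** Record radiation site and date with the tumour assessments. Report any response after radiation separately, as a sensitivity analysis, so that a genuine response in non-irradiated lesions stays visible.

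**Cost.** Protocol wording and one data item, plus an occasional genuine response left out of the primary count. As an illustration on the same assumed scale, take a true rate of 10% and suppose the rule removes 0.5, 1 or 5 percentage points. The chance of stopping at 15 patients then rises from 0.90^15 = 0.206 to 0.905^15 = 0.224, 0.91^15 = 0.243 or 0.95^15 = 0.463. The last case would mean losing half of all responses. The separate report lets the study team see such a case before acting on a 0 of 15 result.
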